
#### Visual Analogue Scale (VAS)

#### Health Status - SF-12

«This survey asks for your views about your health. This information will help keep track of how you feel and how well you are able to do your usual activities. Please answer carefully every question. Some questions may look like others, but each one is different».

(FOR THE INTERVIEWER: Pay attention that the subject answer to all questions, otherwise the test is not valid and the total score cannot be calculated.)

1. «In general, would you say your health is»:

Excellen t	Very good	Good	Fair	Poor
5	4	3	2	1

«The following questions are about activities you might do during a typical day. Does your health now limit you in these activities? If so, how much?»

	Yes, limited a lot	Yes, limited a little	No, not limited at all

 
Moderate activities, such as moving a table, pushing a vacuum cleaner, bowling, or shopping
 
	1	2	□3
3. Climbing several flights of stairs	1	2	3

«During the past week, have you had any of the following problems with your work or other regular daily activities as a result of your physical health?»

	Yes	No
4. Accomplished less than you would like	1	0
5. Were limited in the kind of work or other activities	1	0

«During the past week, have you had any of the following problems with your work or other regular daily activities as a result of any emotional problems (such as feeling depressed or anxious)?»

	Yes	No
6. Accomplished less than you would like	1	0
7. Did work or other activities less carefully than usual	1	0

8. «During the past week, how much did pain interfere with your normal work (including both work outside the home and housework)?»

Not at all	A little bit	Moderately	Quite a bit	Extremely
1	2	3	4	5

«These questions are about how you feel and how things have been with you during the past week. For each question, please give the one answer that comes closest to the way you have been feeling»

«How much of the time during the past week...»

	All of the time	Most of the time	A good bit of the time	Some of the time	A little of the time	None of the time
9. Have you felt calm and peaceful?	1	□2	□3	4	□5	6
10. Did you have a lot of energy?	□1	□2	□3	4	□5	6
11. Have you felt downhearted and blue?	1	 2	□3	4	□5	6

12. «During the past week, how much of the time has your physical health or emotional problems interfered with your social activities (like visiting friends, relatives, etc.)?»

All of the time	Most of the time	A good bit of the time	Some of the time	A little of the time
1	2	3	4	5

#### eHealth Literacy Scale

I would like to ask you for your opinion and about your experience using the Internet for health information. For each statement, tell me which response best reflects your opinion and experience *right now*.

1. How **useful** do you feel the Internet is in helping you in making decisions about your health?

01	02	03	04	05
Not useful at all	Not useful	Unsure	Useful	Very Useful

2. How important is it for you to be able to access health resources on the Internet?

01	02	03	04	05
Not important at all	Not important	Unsure	Important	Very important

- 3. I know what health resources are available on the Internet
- 1) o Strongly Disagree
- 2) o Disagree
- 3) o Undecided
- 4) o Agree
- 5) o Strongly Agree

4. I know where to find helpful health resources on the Internet

- 1) o Strongly Disagree
- 2) o Disagree
- 3) o Undecided
- 4) o Agree
- 5) o Strongly Agree

- 5. I know how to find helpful health resources on the Internet
- 1) o Strongly Disagree
- 2) o Disagree
- 3) o Undecided
- 4) o Agree
- 5) o Strongly Agree

6) I know how to use the Internet to answer my questions about health

- 1) o Strongly Disagree
- 2) o Disagree
- 3) o Undecided
- 4) o Agree
- 5) o Strongly Agree

7) I know how to use the health information I find on the Internet to help me

- 1) o Strongly Disagree
- 2) o Disagree
- 3) o Undecided
- 4) o Agree
- 5) o Strongly Agree

8) I have the skills I need to evaluate the health resources I find on the Internet

- 1) o Strongly Disagree
- 2) o Disagree
- 3) o Undecided
- 4) o Agree
- 5) o Strongly Agree

9) I can tell high quality health resources from low quality health resources on the Internet

- 1) o Strongly Disagree
- 2) o Disagree
- 3) o Undecided
- 4) o Agree
- 5) o Strongly Agree

 $10)\,\mathrm{I}$  feel  $\mathbf{confident}$  in using information from the Internet to make health decisions

- 1) o Strongly Disagree
- 2) o Disagree
- 3) o Undecided
- 4) o Agree
- 5) o Strongly Agree

T1

30-days Rehospitalization rate:

No 🗔

#### Short Physical Performance Battery

#### 1. Repeated Chair Stands

Instructions: Please **stand up straight as quickly as you can five times, without stopping in between**. After standing up each time, sit down and then stand up again. Keep your arms folded across your chest. Please watch while I demonstrate. I'll be timing you with a stopwatch. Are you ready?

Begin Grading: **Begin stop watch when subject begins to stand up**. Count aloud each time subject arises. **Stop the stopwatch when subject has straightened up completely for the fifth time**. Also stop if the subject uses arms, or after 1 minute, if subject has not completed rises, and if concerned about the subject's safety. Record the number of seconds and the presence of imbalance.

- Time: \_\_sec (if five stands are completed)
- Number of Stands Completed: 1234

5 Chair Stand Ordinal Score:

- 0 = unable
- 1 = > 16.7 sec
- 2 = 16.6-13.7 sec
- 3 = 13.6-11.2 sec
- 4 = < 11.1 sec

#### 2. Balance Testing

Begin with a **semitandem stand** (heel of one foot placed by the big toe of the other foot). Individuals unable to hold this position should try the side-by-side position. Those able to stand in the semitandem position should be tested in the full tandem position. Once you have completed time measures, complete ordinal scoring.

#### a. Semitandem Stand

Instructions: Now I want you to try to stand with the **side of the heel of one foot touching the big toe of the other foot for about 10 seconds**. You may put either foot in front, whichever is more comfortable for you.

Please watch while I demonstrate. Grading: Stand next to the participant to help him or her into semitandem position. Allow participant to hold onto your arms to get balance. Begin timing when participant has the feet in position and let's go.

- 2 = Held for 10 sec
- 1 = Held for less than 10 sec; (number of seconds held: \_\_\_\_\_sec)
- 0 = Not attempted

#### b. Side-by-Side stand

Instructions: I want you to try to **stand with your feet together**, **side by side**, **for about 10 sec**. Please watch while I demonstrate. You may use your arms, bend your knees, or move your body to maintain your balance, but try not to move your feet. Try to hold this position until I tell you to stop. Grading: Stand next to the participant to help him or her into the side-by-side position. Allow participant to hold onto your arms to get balance. Begin timing when participant has feet together and let's go.

- 2 = Held of 10 sec
- 1 = Held for less than 10 sec; (number of seconds held: \_\_\_\_\_ sec)
- 0 = Not attempted
- 3. Tandem Stand

Instructions: Now I want you to try to stand with the heel of one foot in front of and touching the toes of the other foot for 10 sec. You may put either foot in front, whichever is more comfortable for you. Please watch while I demonstrate.

Grading: Stand next to the participant to help him or her into the side-by-side position. Allow participant to hold onto your arms to get balance. Begin timing when participant has feet together and let's go.

- 2 = Held of 10 sec
- 1 = Held for less than 10 sec; (number of seconds held: \_\_\_\_\_ sec)
- 0 = Not attempted

Balance Ordinal Score:

- 0 = side by side 0-9 sec or unable
- 1 = side by side 10, <10 sec semitandem
- 2 = semitandem 10 sec, tandem 0-2 sec
- 3 = semitandem 10 sec, tandem 3-9 sec
- 4 = tandem 10 sec

#### 4. 8' Walk (2.44 meters)

Instructions: This is our walking course. If you use a cane or other walking aid when walking outside your home, please use it for this test. I want you to walk at your usual pace to the other end of this course (a distance of 8'). Walk all the way past the other end of the tape before you stop. I will walk with you. Are you ready? Grading: Press the start button to start the stopwatch as the participant begins walking. **Measure the time** take to walk 8'. Then complete ordinal scoring.

Time: sec

Gait Ordinal Score:

- 0 = could not do
- 1 = >5.7 sec (<0.43 m/sec)
- 2 = 4.1-6.5 sec (0.44-0.60
- m/sec)
- 3 = 3.2-4.0 (0.61-0.77 m/sec)
- 4 = <3.1 sec (>0.78 m/sec)

**Summary Ordinal Score**: Range: 0 (worst performance) to 12 (best performance). Shown to have predictive validity showing a gradient of risk for mortality, nursing home admission, and disability.

Visual Analogue Scale (VAS)

Health Status - SF-12

«This survey asks for your views about your health. This information will help keep track of how you feel and how well you are able to do your usual activities. Please answer carefully every question. Some questions may look like others, but each one is different».

(FOR THE INTERVIEWER: Pay attention that the subject answer to all questions, otherwise the test is not valid and the total score cannot be calculated.)

1. «In general, would you say your health is»:

Excellen t	Very good	Good	Fair	Poor
5	4	3	2	1

«The following questions are about activities you might do during a typical day. Does your health now limit you in these activities? If so, how much?»

	Yes, limited a lot	Yes, limited a little	No, not limited at all

 
Moderate activities, such as moving a table, pushing a vacuum cleaner, bowling, or shopping
 
	1	2	3
3. Climbing several flights of stairs	1	2	3

«During the past week, have you had any of the following problems with your work or other regular daily activities as a result of your physical health?»

	Yes	No
4. Accomplished less than you would like	1	0
5. Were limited in the kind of work or other activities	1	0

«During the past week, have you had any of the following problems with your work or other regular daily activities as a result of any emotional problems (such as feeling depressed or anxious)?»

		-
	Yes	No
6. Accomplished less than you would like	1	0 []
7. Did work or other activities less carefully than usual	1	0

8. «During the past week, how much did pain interfere with your normal work (including both work outside the home and housework)?»

Not at all	A little bit	Moderately	Quite a bit	Extremely
1	2	3	4	5

«These questions are about how you feel and how things have been with you during the past week. For each question, please give the one answer that comes closest to the way you have been feeling»

«How much of the time during the past week...»

	All of the time	Most of the time	A good bit of the time	Some of the time	A little of the time	None of the time
9. Have you felt calm and peaceful?	1	2	□3	4	5	6
10. Did you have a lot of energy?	□1	□2	□3	4	□5	6
11. Have you felt downhearted and blue?	 	2	□3	□4	□5	6

12. «During the past week, how much of the time has your physical health or emotional problems interfered with your social activities (like visiting friends, relatives, etc.)?»

All of the time	Most of the time	A good bit of the time	Some of the time	A little of the time
1	2	3	4	5

#### eHealth Literacy Scale

I would like to ask you for your opinion and about your experience using the Internet for health information. For each statement, tell me which response best reflects your opinion and experience *right now*.

1. How **useful** do you feel the Internet is in helping you in making decisions about your health?

01	02	03	04	05
Not useful at all	Not useful	Unsure	Useful	Very Useful

2. How important is it for you to be able to access health resources on the Internet?

01	02	03	04	05
Not important at				
all	Not important	Unsure	Important	Very important

3. I know what health resources are available on the Internet

- 1) o Strongly Disagree
- 2) o Disagree
- 3) o Undecided
- 4) o Agree
- 5) o Strongly Agree

4. I know where to find helpful health resources on the Internet

- 1) o Strongly Disagree
- 2) o Disagree
- 3) o Undecided
- 4) o Agree
- 5) o Strongly Agree

- 5. I know how to find helpful health resources on the Internet
- 1) o Strongly Disagree
- 2) o Disagree
- 3) o Undecided
- 4) o Agree
- 5) o Strongly Agree

#### 6) I know how to use the Internet to answer my questions about health

- 1) o Strongly Disagree
- 2) o Disagree
- 3) o Undecided
- 4) o Agree
- 5) o Strongly Agree
- 7) I know how to use the health information I find on the Internet to help me
- 1) o Strongly Disagree
- 2) o Disagree
- 3) o Undecided
- 4) o Agree
- 5) o Strongly Agree

8) I have the skills I need to evaluate the health resources I find on the Internet

- 1) o Strongly Disagree
- 2) o Disagree
- 3) o Undecided
- 4) o Agree
- 5) o Strongly Agree

- 9) I can tell high quality health resources from low quality health resources on the Internet
- 1) o Strongly Disagree
- 2) o Disagree
- 3) o Undecided
- 4) o Agree
- 5) o Strongly Agree
- 10) I feel confident in using information from the Internet to make health decisions
- 1) o Strongly Disagree
- 2) o Disagree
- 3) o Undecided
- 4) o Agree
- 5) o Strongly Agree

System Usability Scale

The following section relates to your **feelings and thoughts** that may rise while using the **application/device**. Please circle one in each of the following statements, the number that reflects your impressions. There is only one answer possible.

Statement			strongly disagree		↔ stron	
1.	I think that I would like to use the system more often.	1	2	3	4	5
2.	I found the system unnecessarily complex.	1	2	3	4	5
3.	I found the system was easily to handle.	1	2	3	4	5
4.	I think I would need the help of a technical person to be able to use the system.	1	2	3	4	5
5.	I found the different functions in the system were well integrated.	1	2	3	4	5
6.	I think the system were too instable.	1	2	3	4	5
7.	I can imagine that most of the people can easily learn to handle the system very quickly.	1	2	3	4	5
8.	I found the system very uncomfortable to use.	1	2	3	4	5
9.	I felt very safe while using the system.	1	2	3	4	5
10.	I needed to learn a lot of things before I could get going with this system.	1	2	3	4	5

#### Semi-structured interview

ACCEPTANCE	
How often did you use the system during the day?	
Did you feel nervous using the system? Why?	
Did you feel embarrassed using the system in your family? Why?	
What features did you find most useful? And those that you did not like? Do you miss anything?	
Which benefit did it bring to your everyday life?	
Do you think that constant and continued use will benefit you?	
Do you think your anxiety is reduced with the use of the system?	
Do you think there are any risks or negative effects of using the system that we have not discussed?	
Did you enjoy using the system or did you perceive it as an obligation?	
Does the product exactly match your needs? If not, what would you like to see added?	
Do you have concerns about privacy and the use of your data and personal information?	

USABILITY	
What is your impression of the system after using it for this period?	
Did you find the system easy to use? If not, what could make it easier?	
How long did it take you to fully understand the system?	
What actions did you have difficulty with? What took a lot of time to do?	
Do you feel confident while using the system?	
Do you think it is necessary to have technological skills to be able to use the system to its fullest?	

WILLINGNESS TO PAY	
If you imagine the system is on the market, what would help you decide whether or not to purchase it?	
If the system will be launched, how should it be financed?	
How much would you pay the service per month?	
Do you think that such kind of service should be provided/payed by healthcare insurance or national healthcare system?	

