### 6.2. Secondary endpoints

The secondary endpoints are:

- Checking hospital readmission at 60 and 90 days after hospital discharge to evaluate longer term rates.
- Checking how many times the participant possibly got re-hospitalized.
- Improving health status of older person in terms of general quality of life and physical performance. It
  will be accessed through EQ Visual Analogue Scale [26] and Short Form Health Survey 12 items [27] for
  general wellbeing status and Short Physical Performance Battery [23] for physical performance and
  functional status;
- Accessing the usability of the system, to be evaluated through the System Usability Scale [28] to check specific dashboard usability
- Supporting the empowerment of participants in terms of digital/eHealth literacy skills achievement, skills that will be assessed through eHeals scale [29].
- Evaluate acceptability, usability, effectiveness and willingness to pay of the system through semistructured interviews;
- Evaluation of clinical resource utilization through interviews.

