# 7 Protocol

For this pilot study, 210 older adults will be enrolled. The participants will be randomized into 2 groups, respectively 105 cases and 105 controls. The randomization technique based on a single sequence of random assignments is used

A summary of all data collected and when these are collected is provided in Table 5. All scales used are validated in all the national languages of each end-user partner (Italian, Norwegian and Romanian) and suitable for administration for the patients recruited in the study. A complete list of scales are attached as Appendix to the present deliverable.

Scale(s)	R	то	T1	Т2	Т3
Socio-demographic and Anamnesis (Check-list)	$\checkmark$				
MMSE (cognitive)	$\checkmark$				
Short Physical Performance Battery (physical)	$\checkmark$		$\checkmark$	$\checkmark$	$\checkmark$
Clinical Frailty Scale (Frailty)	$\checkmark$				
30-days Rehospitalization rate (y/n)			$\checkmark$		
60-days Rehospitalization rate (y/n)				$\checkmark$	
90-days Rehospitalization rate (y/n)					$\checkmark$
ATDPA – C (Technology attitude)		$\checkmark$			
EQ-5D-5L (only VAS scale) (quality of life)		$\checkmark$	$\checkmark$	$\checkmark$	$\checkmark$
SF-12 short form (4 weeks recall period) ( impact of health in everyday life)		$\checkmark$	√		~
Clinical resource utilization			$\checkmark$	$\checkmark$	$\checkmark$
SUS (Usability of dashboard)			$\checkmark$		$\checkmark$
eHEALS scale (ehealth literacy)		$\checkmark$	$\checkmark$		$\checkmark$
Semi-structured interview on self-management improvement, usability and effectiveness of the system			√		$\checkmark$

Table 5 Clinical assessments and scales divided by different evaluation times

The **Mini Mental State Examination (MMSE)** [22] is a neuropsychological test used to assess cognitive function and detect cognitive impairment; it is particularly useful for monitoring the development of dementia and assessing the cognitive status of patients in clinical settings. Consisting of 30 questions, the test assesses five areas: orientation, registration, attention and computation, recall, language and visuo-constructive skills. The maximum score is 30, with scores below 24 indicating possible cognitive impairment.

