The **eHealth Literacy Scale (eHEALS)** [29] is a 10-item measure of eHealth literacy developed to measure consumers' combined knowledge, comfort, and perceived skills at finding, evaluating, and applying electronic health information to health problems. Advantages include simplicity and speed, in fact it is a short and easy test to administer, suitable for clinical and research settings; user focus, as it focuses on perceptions and subjective abilities, allowing for identification of specific educational needs; and flexibility, as it can be adapted to different populations and cultural contexts.

A **Semi-structured Interview** is adopted to evaluate the perspective on usability, acceptability, effectiveness and willingness to pay. A complete version of interviews is included in the material to be delivered to Ethical Committee for approval.

A **Clinical Resource Utilization** will be used to investigate consumption of health care resources, use of diagnostic tests and specialized clinical procedures, use of care services, and eventual hospital readmission, throughout the study period.

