## Semi-structured interview

ACCEPTANCE	
How often did you use the system during the day?	
Did you feel nervous using the system? Why?	
Did you feel embarrassed using the system in your family? Why?	
What features did you find most useful? And those that you did not like? Do you miss anything?	
Which benefit did it bring to your everyday life?	
Do you think that constant and continued use will benefit you?	
Do you think your anxiety is reduced with the use of the system?	
Do you think there are any risks or negative effects of using the system that we have not discussed?	
Did you enjoy using the system or did you perceive it as an obligation?	
Does the product exactly match your needs? If not, what would you like to see added?	
Do you have concerns about privacy and the use of your data and personal information?	

	Г
USABILITY	
What is your impression of the system after using it for this period?	
Did you find the system easy to use? If not, what could make it easier?	
How long did it take you to fully understand the system?	
What actions did you have difficulty with? What took a lot of time to do?	
Do you feel confident while using the system?	
Do you think it is necessary to have technological skills to be able to use the system to its fullest?	
WILLINGNESS TO PAY	
If you imagine the system is on the market, what would help you decide whether or not to purchase it?	
If the system will be launched, how should it be financed?	
How much would you pay the service per month?	
Do you think that such kind of service should be provided/paid by healthcare insurance or national healthcare system?

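### The interview meant to evaluate effectiveness has no effectiveness block, and its questions on benefit and anxiety lean toward a favourable answer

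*Protocol*

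**What the plan says.** Section 6.2 of the Protocol lists as a secondary endpoint: "Evaluate acceptability, usability, effectiveness and willingness to pay of the system through semistructured interviews". Table 5 in section 7 schedules the tool at T1 and T3 under the label "Semi-structured interview on self-management improvement, usability and effectiveness of the system". The description of instruments in the same section says that the interview "is adopted to evaluate the perspective on usability, acceptability, effectiveness and willingness to pay". Section 8.4 again names effectiveness among the things the investigator's questionnaires and interviews cover at T3.

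The interview form is printed in the Appendix for T1 and again for T3. It has three blocks: Acceptance, Usability and Willingness to pay. Three questions in the Acceptance block bear most directly on what the system did for the patient, and they read the same at both visits:

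- The first concerns daily living: "Which benefit did it bring to your everyday life"
- The second looks ahead to further use: "Do you think that constant and continued use will benefit you"
- The third concerns anxiety: "Do you think your anxiety is reduced with the use of the system"

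The same block also has prompts that point the other way or both ways. These include "What features did you find most useful? And those that you did not like" and, directly after the anxiety question, "Do you think there are any risks or negative effects of using the system that we have not discussed".

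**The concern.** A question meant to show whether an intervention helped should make it as easy to report no change or harm as to report improvement. The first of the three questions asks what kind of benefit there was, not whether there was one. The other two can be answered with a no, but each names only improvement.

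The setting makes agreement with the wording plausible. Under section 8.1 controls receive no technology, and under section 8.2 the T1 evaluation beyond the readmission check is for the experimental group only, so those answering are users of the system. Section 10 says that the platform is supplied without cost to them. Section 8.1 provides for weekly contact about their experience, with technical help when needed. Under section 8.4 the investigator conducts the interview at T3.

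At stake is the effectiveness part of one qualitative secondary endpoint. If most users describe a benefit, the reader cannot tell how far this reflects their experience and how far it reflects the question.

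**Working it through.** No formula applies. The check sets the stated aim beside the printed form and asks what each question can record.

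**Aim against content.** Sections 6.2, 7 and 8.4 all name effectiveness as an aim of the interview. The printed form has no block under that name, so perceived effect has to be read mainly from the Acceptance block.

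**What each question can record.**

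| Patient's experience | Benefit in everyday life | Continued use | Anxiety |
|---|---|---|---|
| Better | described directly | yes | yes |
| No change | patient must contradict the premise | no | no |
| Worse | must be volunteered | no | no |

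- *Benefit in everyday life.* Only this question presupposes its answer. The questions before it cover frequency of use, nervousness, embarrassment and features. None asks whether the system brought a benefit.
- *Continued use.* A no is a complete answer, but it does not distinguish an expectation of no difference from an expectation of burden.
- *Anxiety.* A no is again complete, but it merges unchanged with increased anxiety. If the interviewer does not probe, later coding cannot recover the difference.

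**What the rest of the form adds.**

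- The nervousness prompt concerns feelings while using the system. A patient made anxious by self-monitoring could say so there, but it does not ask about change in anxiety.
- The features prompt is two-sided, as is the one contrasting enjoyment with obligation. Both concern acceptance.
- The Usability block opens with a neutral question on overall impression, which could draw out a view on effect in either direction.
- The question on risks or negative effects does ask about effect in the unfavourable direction. It is limited to matters not yet discussed. That could mean not raised in this interview, or not covered in the training on risks described in section 10.

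These prompts give a patient who got worse somewhere to say so. None of them asks whether there was a benefit before the form asks which benefit it was.

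**Reach.** With 105 participants in the experimental arm (section 7) and two interview visits, at most 105 × 2 = 210 interviews carry this wording.

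**Size.** The protocol gives no coding rule, share or numerical summary for the interview, so there is no estimate to which a bias could be attached. Only its likely direction, upward, can be argued.

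**The case against.** The strongest reply is that the form has to be read whole. It asks about nervousness, embarrassment, dislikes, obligation, privacy concerns and negative effects, and it opens the Usability block neutrally. It is semi-structured with blank answer fields, so no question offers fixed options, an interviewer can probe, and two of the three questions accept a plain no. This largely stands. A reader might infer that the interview is one-sided, or that a patient whose anxiety rose has nowhere to report it. The documents do not support either reading. What remains is narrower: no neutral probe is printed for these three questions, and the presumed benefit is never tested.

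A second reply is that section 7 refers to a complete version of the interviews in the material for the ethics committee. That version is not shown, and it may contain effectiveness questions. Table 5 also names self-management improvement as a topic, and the printed form has no block for that either, which is consistent with a fuller version existing. This is a real limit. If the fuller version is neutral, the Appendix should be aligned with it. If it matches the Appendix, the point holds for both.

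A third reply is that the lack of control answers is not a wording fault. That is correct: controls have no system to report on, and rewording would not change this. Comparative effect is left to readmission, EQ VAS, SF-12 and SPPB. The interview is said to capture the participant's perspective, which is a modest claim.

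**Conclusion.** The point holds as a minor one. An interview with effectiveness among its stated aims has no effectiveness block in its printed form. One question presumes a benefit, and two others name only improvement, so unchanged and worse fall together. Other prompts offset this in part. Any bias in perceived effectiveness is likely to be upward, on the assumption that some participants go along with the wording. Its size cannot be derived from the protocol.

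A reader might go further and conclude that the endpoint is shown to be inflated, or that the trial's evidence of effect is compromised. The documents do not support that. The 30-day readmission endpoint, the sample size, and the usability and willingness-to-pay results do not depend on these questions. The verdict also assumes that the printed form is the one that will be used.

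**What to change.** Reword the three questions on both the T1 and the T3 form, for example:

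- *Did the system change anything in your everyday life: for better, for worse, or no change, and how?*
- *Would continued use help you, make no difference or be a burden?*
- *Since using the system, is your anxiety lower, the same or higher?*

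Each answer can then be recorded as better, same or worse, with the free text kept. Check the complete version referred to in section 7 and align it with the Appendix, so that one wording is used at all sites and both visits.

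The cost is translation into Italian, Norwegian and Romanian and notification of the ethics committees. No visit, instrument or participant is added. The change is best made before the first T1 interview, so that all participants answer the same questions.
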